2.3 Endpoints

2.3.1 Primary endpoints

Stage 1:

- Safety and tolerability following single dose of CBL-514 as assessed by recording of TEAEs, laboratory assessments, vital signs, ECGs, physical examinations, and injection site assessment.

Stage 2:

- The proportion of subjects who lose at least 150 mL of subcutaneous fat as measured by ultrasound from Baseline to follow-up visits compared with placebo. [Time frame: Visit 2 (Baseline), Visit 6, and Visit 7]

2.3.2 Secondary endpoints(s)

Stage 1:

- Reduction of subcutaneous fat thickness as measured by ultrasound compared with Baseline. [Time frame: Day 1 and Week 4]
- Reduction of subcutaneous fat volume over the treated area as measured by ultrasound compared with Baseline. [Time frame: Day 1 and Week 4]

*Note: no efficacy endpoints/objectives will be assessed for Group 1 of Stage 1 study.

Stage 2:

- Reduction of subcutaneous fat volume over the treated area as measured by ultrasound from Baseline to follow-up visits compared with placebo. [Time frame: Visit 2 (Baseline), Visit 6, and Visit 7]
- Reduction of subcutaneous fat volume over the treated area of the CBL-514 group as measured by ultrasound compared with individual Baseline. [Time frame: Visit 2 (Baseline), Visit 3, Visit 4, Visit 5, Visit 6, and Visit 7]
- Number of treatments required to first occurrence of reducing at least 150 mL of subcutaneous fat volume over the treated area as measured by ultrasound in CBL-514 group. [Time frame: from Visit 2 (Baseline) to Visit 7]
- The proportion of subjects who lose at least 200 mL of subcutaneous fat as measured by ultrasound from baseline to follow-up visits compared with placebo. [Time frame: Visit 2 (Baseline), Visit 6, and Visit 7]
- Safety as assessed by recording of TEAEs, laboratory assessments, vital signs, ECGs, physical examinations, and ISRs compared with placebo

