- Subjects who complete all proposed dosing schedules of study drug and complete 2 follow-up visits after treatment (including the subject who has dose adjustment judged by the Investigator)
- Subjects have all visits of IP administration within 6 weeks.
- Subjects whose body weight remain stable throughout the study, identified as having body weight change < 2.5 kg compared to last visit and change of body weight < 3 kg compared to Day 1 body weight.
- Subjects whose Visit 6 is performed 3 to 5 weeks post final treatment
- Subjects whose Visit 7 is performed 7 to 9 weeks post final treatment

However, a subject who was discontinued due to an AE, or died before the required exposure could be met, will still be included in this population.

Safety and Tolerability Assessment

Safety and Tolerability assessment is the primary objective of Stage 1 of the study and secondary objective of Stage 2 of the study.

All safety assessments, including AEs, laboratory evaluations, vital signs, ECGs, physical examination, ISR and other safety assessments, will be analyzed using the Safety population.

- AEs will be coded using the most current version of the Medical Dictionary for Regulatory Activities (MedDRA®) available at the start of the study. A by subject AE data listing, including verbatim term, Preferred Term (PT), System Organ Class (SOC), treatment, severity, and relationship to IP, will be provided. The number of subjects experiencing TEAEs and number of individual TEAEs will be summarized among treatment groups (or sequences), by SOC and PT. TEAEs will also be summarized among treatment groups (or sequences), by severity and by relationship to IP.
- Clinical laboratory tests and vital signs of observed values and changes from Baseline will be summarized using descriptive statistics. Physical examination findings, injection site assessments, and ECGs will also be summarized descriptively.

Safety data from Stage 1 will be reviewed during the SRC meeting before commencement of Stage 2 of the study. A top-level summary of safety data will be submitted to the relevant IEC/IRB for review

before proceeding to Stage 2 of the study.

Efficacy Assessments

Efficacy will be analyzed in both Stage 1 and Stage 2 of the study.

Stage 1

Efficacy endpoints to be analyzed in Stage 1 are:

- Reduction of subcutaneous fat thickness as measured by ultrasound compared with Baseline

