6.2.2. Clinical Studies

The safety and tolerability of injection lipolysis with CBL-514, PK profile of and preliminary efficacy of 4 doses of CBL-514 in reducing abdominal subcutaneous fat at the target area was evaluated in a first-in-human, placebo-controlled, double-blind, Phase 1/2a study (CBL-16001) in Australia. In the Phase 1 component of CBL-16001, CBL-514 was administered in human for the assessment of safety and tolerability. The treatment was a SAD design in which 9 proposed dosing cohorts were involved (Cohorts 1 to 9). In 9 sequential cohorts, CBL-514 dose levels were 2 mg, 10 mg, 20 mg, 40 mg, 40 mg, 80 mg, 160 mg, 240 mg, and 320 mg per subject. For Cohorts 1 to 5, both CBL-514 and placebo groups were administered on each side of abdomen in a blinded manner to evaluate the possible AEs attributed to the components of CBL-514. For Cohorts 6 to 9, only CBL-514 was dosed in subjects.

Overall, Phase 1 results in physical examination, vital signs, ECG, and laboratory tests, including biochemistry, hematology, coagulation, and urinalysis, all showed favorable profiles for the safety of CBL-514. While there was no systemic TEAE from CBL-514, the most frequent TEAEs were ISRs.

[REDACTED]

[REDACTED]

In the Phase 1 component of CBL-16001, CBL-514 was well tolerated through the ascending dose escalation scheme from 2 mg to 320 mg.

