6.4.1. Rationale for Dose Selection

The maximum dose of this Phase 2 study is estimated based on the 8-week repeated-dose GLP toxicity studies in Sprague-Dawley rats and Beagle dogs, respectively.

[REDACTED]

[REDACTED]

[REDACTED]

[REDACTED]

[REDACTED]

[REDACTED]

[REDACTED]

[REDACTED]

[REDACTED]

[REDACTED]

[REDACTED]

Furthermore, the completed Phase 1/2a Study (protocol number: CBL-16001) had evaluated the safety of CBL-514 injection for reducing abdominal subcutaneous fat. Single treatment of CBL-514 were administered with dose levels of 2 mg, 10 mg, 20 mg, 40 mg, 80 mg, 160 mg, 240 mg, and 320 mg per subject, which have shown overall favorable results in physical examination, vital signs, ECG, laboratory tests including biochemistry, hematology, coagulation, and urinalysis profiles.

There was no systemic TEAEs from CBL-514, the most frequent TEAEs were ISRs. During SAD progress, the severity and duration of common ISRs did not show apparent difference among cohorts, which provided even more evidence on the safety of CBL-514 in human.

Based on the nonclinical and clinical results above, the dose escalation groups in the present study are structured as 320 mg, 480 mg, 640 mg, and 800 mg to assess safety and tolerability of higher doses of CBL-514 when injected in abdominal or thigh adipose tissue.

The doses used in this study are 2 mg/cm², which are all within the pharmacologically active dose range. (Please refer to IB for more details) Moreover, the Phase 1 component of CBL-16001 study have assessed safety in human from 0.5 ~ 2 mg/cm² with favourable safety profiles. Based on the results of the CBL-16001 Phase 1 study, the incidence of TEAEs reported were similar across all dose cohorts especially in Cohort 5 to 9, where subjects received the same unit dose (2 mg/cm²) over an increasing treatment area/ total dose per Cohort. Therefore, CBL-0202 has adopted the similar design to have a consistent unit dose, 2 mg/cm², throughout the study. It is expected that the severity or incidence of adverse events in CBL-0202 study will not increase compared to the completed study, even though the dose used is higher.

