11.1 Adverse Events

AEs and serious AEs (SAEs) are defined in the study protocol.

Treatment Emergent Adverse Events (TEAEs) are defined as adverse events that occurred following the first administration of study medication. If missing dates or time prevent a clear determination as to whether the AE is treatment emergent, the adverse event will be regarded TEAE.

All AE verbatim terms will be coded using the most recent version of MedDRA. All AE summaries will be restricted to include TEAEs only. AEs occurring prior to first dose of study medication will be listed but not included in any tabulations. Summary tables will include the number of participants (%) experiencing an event and the number of events. Participants will be counted only once for each SOC and PT level (categorical descriptive analysis).

The TEAE summaries will include:

- Overall summary of TEAEs.
- Summary of TEAEs by SOC, PT and Relationship.
- Summary of TEAEs by SOC, PT and Severity.
- Summary of Definitely Related TEAEs by SOC, PT and Severity
- Summary of Probably or Possibly Related TEAEs by SOC, PT and Severity
- Summary of TEAEs of Special Interest by SOC, PT and Severity
- Summary of serious TEAEs by SOC and PT.
- Summary of Treatment Related serious TEAEs by SOC and PT
- TEAE summary of events leading to the study drug withdrawal by SOC and PT.
- Treatment Related TEAE summary of events leading to the study drug withdrawal by SOC and PT

For the 'Overall Summary of TEAEs', the following items will be included:

1. Any TEAEs
2. Any serious TEAEs
3. Any TEAEs leading to study discontinuation
4. Any TEAEs of special interest
5. Any related TEAE
6. Any TEAEs leading to study discontinuation
7. Any TEAEs leading to death

All AEs will be listed and will include the start and stop date and time of AEs, AE number, verbatim term, Preferred Term, System Organ Class, SAE/TEAE flag, actions taken for AE, relationship to study treatment and outcome.

Separate by-participant data listings will be created for SAEs, AEs leading to study discontinuation, and AEs leading to death. These listings will be presented by participant ID and AE start date/time for the Safety Population.

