13. CHANGES TO THE PLANNED ANALYSIS

Not applicable.

14. INTERIM AND FINAL ANALYSIS**14.1 Interim Analysis**

No Interim analysis planned for this study.

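### Injection-site reactions are a named safety endpoint in both stages, but the SAP tabulates them only as separate preferred terms and plans no any-ISR rate by arm and no summary of injection-site assessments

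*SAP*

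**What the plan says.** **Endpoints.** SAP 2.3.1 defines the Stage 1 primary endpoint as safety and tolerability. After TEAEs it names "laboratory assessments, vital signs, ECGs, physical examinations, and injection site assessment". SAP 2.3.2 gives the Stage 2 secondary safety endpoint as "Safety as assessed by recording of TEAEs, laboratory assessments, vital signs, ECGs, physical examinations, and ISRs compared with placebo". Both name the injection-site item separately from TEAEs.

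**Known harm.** Protocol 6.2.2, on the earlier Phase 1 component, states that "the most frequent TEAEs were ISRs". Protocol 6.4.1 repeats this in the dose rationale: "There was no systemic TEAEs from CBL-514, the most frequent TEAEs were ISRs".

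**What the protocol promises.** The synopsis says "Physical examination findings, injection site assessments, and ECGs will also be summarized descriptively". Protocol 16.2 adds that ISRs will be analyzed in the Safety population. Protocol 14.1.4 has ISRs recorded as adverse events and graded by CTCAE version 5.0.

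**What the SAP plans.** Section 11 has subsections on adverse events, laboratory tests, vital signs, ECG, physical examination and pregnancy/FSH. It has none on ISRs or injection-site assessments. The counting rule for adverse events in 11.1 is "Participants will be counted only once for each SOC and PT level (categorical descriptive analysis". Section 17 names no ISR or injection-site table or listing. Section 13, on changes to the planned analysis, reads "Not applicable".

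**The concern.** The endpoint is about subjects: how many on each arm had an injection-site reaction. The SAP supplies terms instead, such as pain, swelling and bruising, each on its own row. For a subcutaneous product given as up to 50 injections per treatment and up to four treatments, a reader of the study report will look first for the proportion of subjects with any ISR, by arm and by worst grade. As written, no planned table gives that figure.

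The second gap is the scheduled assessments. Sites examine the injection site at every Stage 2 visit from Visit 2 onward, both before and after dosing at Visits 2 to 5, and at every Stage 1 visit from Day 1. These findings are part of the Stage 1 primary endpoint, and the synopsis says they will be summarized. The SAP does not name an output for them and does not say that the summary was dropped.

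Timing also matters. Under Protocol 10.7 the investigator, site staff and sponsor know the allocation in Stage 2. An ISR grouping first chosen while the report is being written would be open to the criticism that it was chosen with the arm results in view.

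**Working it through.** The plan gives no figure to reproduce, so this is a comparison of documents plus one counting argument.

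**Step 1. Each endpoint component against its SAP output**

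| Component named in SAP 2.3.1 / 2.3.2 | SAP section | Named output in SAP 17 |
|---|---|---|
| TEAEs | 11.1 | Tables 14.3.3.x, Listings 16.2.7.x |
| Laboratory assessments | 11.2 | Tables 14.3.4.x and 14.3.5.1.x, Listings 16.2.8.x |
| Vital signs | 11.3 | Tables 14.3.5.2.x, Listing 16.2.9.1 |
| ECGs | 11.4 | Tables 14.3.5.3.x, Listing 16.2.9.2 |
| Physical examinations | 11.5 | Listing 16.2.9.3 |
| Injection-site assessment / ISRs | none | none |

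The injection-site item is the only component with neither a section nor a named output.

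**Step 2. Where ISRs do appear**

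Stage 2 has ten TEAE tables, 14.3.3.1.2 to 14.3.3.10.2. One is the overall summary, and the other 10 − 1 = 9 are by SOC and preferred term. Because ISRs are recorded as adverse events, any ISR that starts after first dose is a TEAE. It will therefore be found, by treatment group, at least in Table 14.3.3.2.2 (by relationship) and Table 14.3.3.3.2 (by severity), with subject and event counts. Local reactions that meet an AESI definition also enter Table 14.3.3.6.2. Tables specific to ISRs: 0 of 10. The Stage 1 set has the same structure and the same count.

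**Step 3. Why term rows do not give the subject-level rate**

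Let n₁, …, n_k be the numbers of subjects in one arm with each of k ISR preferred terms. Each subject counts once per term, so a subject with three terms is in three rows. The number with at least one ISR, U, is only bounded:

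- max(nᵢ) ≤ U ≤ min(Σnᵢ, T), where T is the number of subjects with any TEAE, taken from the overall table.
- If every ISR term falls in one SOC, that SOC's subject count is a further upper bound. It equals U only if no subject is counted in that SOC solely because of non-ISR terms, and the SAP does not ensure this.

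The documents contain no ISR rates, so the width of this interval cannot be calculated from them. The bounds do show that U is not generally recoverable from the planned tables.

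**Step 4. Is the information collected?**

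Yes. Protocol 14.2.1 and 14.2.6 record onset, resolution and severity for each event. SAP 11.1 puts start and stop dates and times, preferred term and SOC in the adverse-event listing. SAP section 8 lists dosing dates and times. What is missing is a planned tabulation.

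**The case against.** The strongest reply is that ISRs are already analyzed. They are CTCAE-graded adverse events and appear with percentages by arm, severity and relationship. Several prolonged local reactions are AESIs defined by persistence thresholds and have their own table. SAP section 11 says generally that safety endpoints will be summarized descriptively, and SAP 3.1 says all eCRF data will be listed. The mock shells are not among the documents and might contain an ISR row. The subsections of Protocol 16.2 define no ISR table either, so the only explicit promise of a summary is one synopsis sentence.

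Much of this stands. A reader might infer that no comparison of ISRs with placebo can be read from any planned table, or that the trial could not state an ISR rate or duration. The documents do not support either reading: term-level comparison is planned, and subject-level counts and durations could be derived from the listed data. A reader might also infer that the endpoints require duration or per-course summaries. Neither endpoint asks for them, and the mention of ISR duration in Protocol 6.4.1 describes the earlier study.

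The reply does not close the gap. The general sentences define no ISR grouping and no display. The AESI table covers only events that meet its definitions, not ordinary ISRs. No text plans an ISR row in a shell. Rebuilding an endpoint by hand from listings is not a pre-specified analysis.

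**Conclusion.** The point holds as a tabulation gap that should be corrected. The most frequent known harm, named as an endpoint in both stages, is spread over separate preferred terms. No grouping is defined, no any-ISR proportion by arm is planned, and no output is named for the scheduled injection-site assessments. SAP section 13 does not acknowledge that the promised summary is absent. Protocol section 16 lets the SAP prevail where the two diverge. Whether silence amounts to divergence is arguable, and that is a further reason to state the intention.

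The size is 0 ISR-specific tables among the ten Stage 2 TEAE tables and no named injection-site listing. No percentage-point consequence can be given without ISR rates, which the documents do not supply. The conclusion rests on the SAP text and output index being the full plan; an unpublished shell with an any-ISR row would remove part of it. It implies no data loss and does not touch the efficacy analysis.

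**What to change.** Before database lock:

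1. Pre-list in SAP section 11 the preferred terms that count as ISRs, or use an eCRF ISR flag if one exists. Since the sponsor and sites know the allocation, the list should be agreed without reference to arm-level results where possible.
2. Add to SAP sections 11 and 17 one table per stage, on the Safety population and by treatment group, showing subjects with at least one ISR overall and by maximum severity.
3. In the Stage 2 table, add the CBL-514 minus placebo difference in the any-ISR proportion with a 95% CI, labelled descriptive, using an interval method named in advance. This fits the plan's position that no formal hypothesis testing is done.
4. Add a summary or a named listing of the scheduled injection-site assessments. If the separate summary has been dropped on purpose, say so and why in SAP section 13.

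ISR duration and ISRs by treatment course are optional additions, available from the adverse-event and dosing dates already collected.

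The cost is SAP wording, agreement on a term list, one extra table per stage and one assessment output. No new data are needed and clinical management does not change.

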2.4 Sample Size

Approximately 99 adult male or female subjects, will participate in the study. A total of 24 subjects are planned to be enrolled in 4 sequential groups in Stage 1 of the study. Considering drop-out rates, approximately 75 subjects are planned to be enrolled and randomized 2:1 (i.e., 50 subjects in the CBL-514 group and 25 subjects in the placebo group) in order to have 56 evaluable subjects in Stage 2 of the study. The sample size for stage 2 of the study was calculated based on currently accepted standards for exploratory investigation design.

2.5 Randomization

Stage 1 of the study will be open label with a total of 24 subjects sequentially enrolled in 4 dose groups (6 subjects in each group) to receive one course of allocated CBL-514 dose as presented in Table 1. Once deemed eligible for enrolment in the study, each subject will be assigned a sequential subject number prior to first dosing.

Stage 2 of the study will be a randomized, single-blind, parallel-group. Considering drop-out rates (16% CBL-514 group vs 44% placebo group), approximately 75 subjects are planned to be enrolled and randomized 2:1 (50 subjects in the CBL-514 group and 25 subjects in the placebo group) in order to have a total of at least 56 evaluable subjects in Stage 2 of the study. The dose of CBL-514 used in Stage 2 will be set no higher than the highest safe dose from Stage 1. Once deemed eligible for enrolment in the study, each subject will be assigned a sequential randomization number prior to first dosing.

3. STATISTICAL CONSIDERATIONS

Data will be handled and processed per the sponsor's representative [REDACTED] Standard Operating Procedures (SOPs), which are written based on the principles of good clinical practice (GCP).

3.1 General Considerations

All data collected on the electronic case report form (eCRF) will be presented in the data listings and will be listed and sorted by treatment arm participant number and visit, where applicable. All descriptive summaries will be presented by treatment group and nominal visit/time point (where applicable).

Unless otherwise stated, the following methods will be applied:

- Continuous variables: Descriptive statistics will include the number of non-missing values (n), arithmetic mean, standard deviation (SD), median, minimum and maximum values.

The minimum and maximum values will be displayed to the same decimal precision as the source data, the arithmetic mean, SD and median values will be displayed to one more decimal than the source data for the specific variable.

95% Confidence Intervals (CIs), mean differences (among treatments and from baseline) and least-square (LS-Means) values will be displayed to one more decimal than the source data for a specific variable. P-values will be displayed to 5 decimal places.

The appropriate precision for derived variables will be determined based on the precision of the data on which the derivations are based, and statistics will be presented in accordance with the above mentioned rules.

- Categorical variables: Descriptive statistics will include counts and percentages per category. The denominator in all percentage calculations will be the number of participants in the relevant analysis population with non-missing data, unless specifically stated otherwise. Percentages will be displayed to one decimal place. Proportions will be displayed to 3 decimal places.

95% Confidence Intervals (CIs), difference in proportions, and other categorical parameters will be displayed to one decimal place for percentages. Proportions will be displayed to 3 decimal places. P-values will be displayed to 5 decimal places.

- Repeat/unscheduled assessments: Only values collected at scheduled study visits/time points will be presented in summary tables. If a repeat assessment was performed, the result from the original assessment will be presented as the result at the specific visit/time point. All collected data will be included in the data listings.
- Assessment windows: All assessments will be included in the data listings and no visit windows will be applied to exclude assessments that were performed outside of the protocol specified procedure windows.
- Result display convention: Results will be center aligned in all summary tables and listings. Participant identifiers visit and parameter labels may be left-aligned if required.
- Date and time display conventions: The following display conventions will be applied in all outputs where dates and/or times are displayed:

Date only: YYYY-MM-DD

Date and time: YYYY-MM-DD HH:MM

If only partial information is available, unknown components of the date or time will be presented as 'NK' (not known), i.e., '2016-NK-NK'. Times will be reported in military time.

